##### **AEs of special interest (AESIs):**

AESIs will be collected throughout the study (D0 through V3). AESIs will have the same detailed information collected as SAEs. Each AESI will be retrieved using the following (as shown in [Table 7](#)):

**Table 7 – AESI PTs**

AESI	PT
Guillain-Barré syndrome (GBS)	Chronic inflammatory demyelinating polyradiculoneuropathy Demyelinating polyneuropathy Guillain-Barre syndrome Miller Fisher syndrome
encephalitis/myelitis (including transverse myelitis)	Myelitis Myelitis transverse Encephalitis is using the narrow SMQ term “Noninfectious encephalitis” (Medical Dictionary for Regulatory Activities [MedDRA] Version 20.1)
Bell’s palsy	Facial palsy Facial paralysis Facial paresis Bell’s palsy
optic neuritis	Optic neuritis Optic neuropathy
brachial neuritis	Brachial neuritis Brachial plexopathy Neuralgic amyotrophy Parsonage Turner Syndrome

### 2.5.3 Data handling conventions for immunogenicity variables

#### 2.5.3.1 Computed values for analysis

In order to appropriately manage replicate values for analysis purpose, the individual GMT of all values will be computed for each blood sample after managing extreme values as described. The computed value is then considered the titer for that particular blood sample.

- If a titer is <LLOQ, then the computed value, LLOQ/2, will be used
- If a titer is  $\geq$ LLOQ and <ULOQ (or  $\leq$ ULOQ), then the titer itself will be used
- If a titer is  $\geq$ ULOQ (or >ULOQ), then computed value, ULOQ, will be used.

No test or search for outliers will be performed.

#### 2.5.3.2 Seroprotection

If the computed value of HAI titer  $\geq$ 40 [1/dil], then the derived seroprotection indicator will be “Yes” for that test, otherwise seroprotection will be “No”.

Note: If the computed value is missing, seroprotection indicator will be missing.

### **2.5.3.3 Fold-rise**

The derived endpoint fold-rise is driven by both baseline and post-vaccination computed values which are computed as described in [Section 2.5.3.1](#). The computed value for fold-rise is:

$$\text{Computed value} = \text{Post-vaccination computed value} / \text{Baseline computed value.}$$

For HAI assay, if the computed value is  $\geq 4$ -fold rise, then the derived 4-fold rise indicator will be “Yes” for that test, otherwise the corresponding indicators will be “No”. If baseline or post-vaccination value is missing, then the fold-rise is missing.

### **2.5.3.4 Seroconversion**

Seroconversion is defined for HAI assay as either

- A computed value of HAI titer  $< 10$  [1/dil] at D0 and post-injection titer  $\geq 40$  [1/dil] at D28
- A computed value of HAI titer  $\geq 10$  [1/dil] at D0 and a  $\geq 4$ -fold increase in HAI titer [1/dil] at D28

## **2.5.4 Missing data**

For categorical variables, patients with missing data are not included in calculations of percentages unless otherwise specified. When relevant, the number of patients with missing data is presented.

### ***Handling of safety data***

In general, no replacement will be done.

Nevertheless, missing relationship will be considered as related at the time of statistical analysis. No search for outliers will be performed. In all subject listings, partial and missing data will be clearly indicated as missing.

### ***Handling of medication missing/partial dates***

No imputation of medication start/end dates or times will be performed. If a medication date or time is missing or partially missing and it cannot be determined whether it was taken prior or concomitantly, it will be considered a prior, concomitant, and post-treatment medication.

### ***Handling of adverse events with missing or partial date/time of onset***

Missing or partial missing start dates for unsolicited AEs will remain missing and not be imputed. If either the start or stop date is missing or partially missing, the time of onset will be considered to be missing. Nevertheless unsolicited AEs with missing time of onset will be included in analyses according to the visit collected.

Missing or partially missing stop dates for AEs (solicited reactions and unsolicited AEs) will remain missing and not be imputed.

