#### **2.1.4.1.2.3 Unsolicited Adverse Events**

In addition to recording solicited reactions, subjects will be instructed to record any other medical events that may occur during the 28-day period after vaccination. Space will be provided in the diary card for this purpose.

Information on SAEs will be collected and assessed throughout the study, from inclusion until 28 (+ 7) days after vaccination. Any SAE occurring at any time during the study will be reported by the Investigator in the CRB according to the completion instructions provided by the Sponsor; this includes checking the “Serious” box on the AE CRF and completing the appropriate Death/Safety Complementary Information CRFs. All information concerning the SAE is to be reported either as part of the initial reporting or during follow-up reporting if relevant information became available later (e.g., outcome, medical history, results of investigations, copy of hospitalization reports). See Section 10 of the protocol for further details on SAE reporting.

For each unsolicited AE (whether serious or non-serious), the following information is to be recorded:

- Start and stop dates
- Intensity of the event

For measurable unsolicited AEs that are part of the list of solicited reactions, the size of the AE as well as the temperature for fever will be collected and analyzed based on the corresponding scale used for solicited reactions (see [Table 2](#) and [Table 3](#)).

All other unsolicited AEs will be classified according to the following intensity scale:

- Grade 1: A type of AE that is usually transient and may require only minimal treatment or therapeutic intervention. The event does not generally interfere with usual activities of daily living.

---

 The stop date of all related AEs will be actively solicited. For other events, the investigator will provide the stop date when it becomes available. AEs for which no stop date was obtained during the course of the study will be considered as ongoing at the end of the study.

- Grade 2: A type of AE that is usually alleviated with additional therapeutic intervention. The event interferes with usual activities of daily living, causing discomfort but poses no significant or permanent risk of harm to the research participant.
- Grade 3: A type of AE that interrupts usual activities of daily living, or significantly affects clinical status, or may require intensive therapeutic intervention.

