#### **Time of onset:**

Time of onset is derived from the start date of the unsolicited non-serious AE provided in the clinical database and the date of last vaccination:

Start date of the unsolicited non-serious AE – date of vaccination.

The time of onset should be considered as missing only if one or both of the dates are missing or partially missing.

The unsolicited non-serious AEs will be analyzed “Within 28 days”, which corresponds to AEs with a time of onset between 0 and 28 days after vaccination or missing. An AE with missing time of onset will be considered to have occurred just after the vaccination indicated by the visit number, so will be included in these tables.

Note: Unsolicited non-serious AE that occurred before vaccination (negative time of onset) or with a time of onset higher than defined above (>28 days) will not be included in analysis, but will be listed separately.

Time of onset will be displayed as follows:

- D0-D3
- D4-D7

- D8-D14
- $\geq$ D15
- Missing

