**Duration:**

Duration is derived from the start and stop dates of the unsolicited non-serious AE provided in the clinical database:

Stop date of unsolicited non-serious AE – start date of unsolicited non-serious AE + 1.

The duration should be considered as missing only if one or both of the start and stop dates of the unsolicited non-serious AE is missing or partially missing.

Duration will be displayed by period as following:

- 1-3 days
- 4-7 days
- 8-14 days
- $\geq$ 15 days
- Missing

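### SAP 2.5.4 sets an unsolicited AE's time of onset to missing when only the stop date is absent, which contradicts SAP 2.5.2.2 and would misplace known onsets

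*SAP*

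**What the plan says.** Two parts of the SAP define when the onset of an unsolicited AE is missing.

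- **SAP 2.5.2.2, Time of onset.** Onset is "derived from the start date of the unsolicited non-serious AE provided in the clinical database and the date of last vaccination", computed as start date minus vaccination date. On missingness: "The time of onset should be considered as missing only if one or both of the dates are missing or partially missing". The stop date is not an input.
- **SAP 2.5.4, Handling of adverse events with missing or partial date/time of onset.** "If either the start or stop date is missing or partially missing, the time of onset will be considered to be missing". It goes on to say that "unsolicited AEs with missing time of onset will be included in analyses according to the visit collected", and that stop dates are not imputed.

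Three other rules determine what follows from the difference.

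- **28-day tables (2.5.2.2).** These take "AEs with a time of onset between 0 and 28 days after vaccination or missing". An AE "with a time of onset higher than defined above (>28 days) will not be included in analysis, but will be listed separately".
- **Duration (2.5.2.2).** "The duration should be considered as missing only if one or both of the start and stop dates" is missing or partial. The stop date therefore already has a place in the duration rule.
- **Absent stop dates (2.1.4.1.2.3, footnote 1).** "AEs for which no stop date was obtained during the course of the study will be considered as ongoing" when the study ends. The same footnote says stop dates of related AEs are actively sought.

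**The concern.** An ongoing AE with a fully recorded start date has a known onset under 2.5.2.2 and a missing one under 2.5.4. The words *only if* in 2.5.2.2 rule out the additional trigger in 2.5.4. The two cannot be read as a general rule and its exception, because both govern the same variable for the same AEs.

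Time to onset is a named safety endpoint (SAP 2.1.4) and a planned summary of unsolicited non-serious AEs (SAP 2.4.4.1). Programming 2.5.4 would have two effects.

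1. A known onset leaves its true row of the onset table for *Missing*. Late onsets are the most exposed, since they have the least time to resolve before V3.
2. Missing onset counts as within 28 days, whereas a known onset after D28 is excluded. Whether a late AE is counted would then depend on whether it had ended, not on when it began.

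Neither effect arises if 2.5.2.2 is programmed.

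**Working it through.** The plan gives no figure to reproduce here. The check applies both rules to every possible onset day.

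**Inputs**
- Onset rows D0-D3, D4-D7, D8-D14, D15 and later, Missing (SAP 2.5.2.2). Within D0-D28 the first four rows hold 4 + 4 + 7 + 14 = 29 days.
- V3 at D28 with a window of +7 days, so D28 to D35; one vaccination (SAP Table 1).
- Unsolicited AEs collected up to V3 (SAP 1.1).

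**Rules**
- 2.5.2.2: onset = start date − vaccination date; missing only if one of those two is incomplete.
- 2.5.4: as above, but also missing if the stop date is incomplete.
- 28-day tables: include if onset is 0 to 28 or missing.

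**Result for an AE with a complete start date**

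| Stop date | V3 on | Onset days possible | Days where the row differs (D0-D28) | Days where 28-day inclusion differs |
|---|---|---|---|---|
| Incomplete | D28 | 29 | 29 | 0 |
| Incomplete | D31 | 32 | 29 | 3 |
| Incomplete | D35 | 36 | 29 | 7 |
| Complete | any of these | 29, 32 or 36 | 0 | 0 |

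These are counts of onset days, not of AEs. Examples:
- Start D10, no stop date: row D8-D14 under 2.5.2.2, *Missing* under 2.5.4; counted under both.
- Start D31, no stop date: excluded under 2.5.2.2, counted under 2.5.4.
- Start D31, stop D33: excluded under both.
- Recorded start one day before vaccination, no stop date: excluded under 2.5.2.2, counted under 2.5.4.

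**Which rows are most exposed**

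Days available from onset to V3 run from 28 − last day of the row to 35 − first day of the row:

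| Row | Minimum | Maximum |
|---|---|---|
| D0-D3 | 28 − 3 = 25 | 35 − 0 = 35 |
| D4-D7 | 28 − 7 = 21 | 35 − 4 = 31 |
| D8-D14 | 28 − 14 = 14 | 35 − 8 = 27 |
| D15-D28 | 28 − 28 = 0 | 35 − 15 = 20 |

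**Illustration on assumed figures**

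Assume exponential AE duration with median m, onset spread evenly over the days of a row, and no stop date added after V3. The share without a stop date is then the mean over the row's days of 0.5^((V3 − day)/m).

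| Median m | D15-D28, V3 on D28 | D15-D28, V3 on D35 | D0-D3, V3 on D28 | D0-D3, V3 on D35 |
|---|---|---|---|---|
| 3 days | 33.3% | 6.6% | 0.2% | 0.0% |
| 7 days | 56.8% | 28.4% | 7.3% | 3.6% |
| 14 days | 73.9% | 52.3% | 27.0% | 19.1% |

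The durations are not trial data. The table shows only that the loss would be concentrated in late onsets.

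**The case against.** The strongest reply is that this is a drafting slip with little practical effect. SAP 2.5.2.2 holds the operative formula, SAP 2.5.2.3 refers SAE onset back to it, and the start/stop wording plainly fits duration. Where 2.5.4 is meant to govern a derived variable, as for causality, the SAP points to it; the onset rule has no such pointer. A programmer who follows the formula gets the right answer. These signals favour 2.5.2.2, but they do not settle precedence, and 2.5.4 is the section headed for missing or partial dates.

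Several limits on the size do stand:
- Non-serious AEs with onset D0-D28 are counted under either rule, so their 28-day incidence, SOC/PT and intensity counts do not change.
- Onsets on D29-D35 need V3 after D28. They are probably few, since subjects are told to record events over 28 days.
- Mainly unrelated AEs are exposed, because stop dates of related AEs are actively sought and those AEs are followed beyond the study. The illustration ignores this.
- Solicited reactions are unaffected; their onset comes from daily intensities (SAP 2.5.2.1).
- The footnote shows that absent stop dates are foreseen, not that they are common.

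The clause in 2.5.4 that includes missing-onset AEs by visit collected does not close the gap. The SAP defines no visit-based period that would remove AEs starting after D28, and with one vaccination 2.5.2.2 places them just after it.

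**Conclusion.** The concern holds. The two SAP rules contradict each other for any unsolicited AE with a complete start date and an incomplete stop date. If 2.5.4 is programmed, the onset row is wrong for such an AE on all 29 onset days D0-D28, and 28-day inclusion is wrong on 0 to 7 further onset days, depending on V3. With a complete stop date the rules never differ.

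The number of AEs affected cannot be calculated, because the documents give neither an AE rate nor the share without a stop date. The main consequence is for the onset table; the post-D28 effect is secondary. All analyses are descriptive, so no test result is at stake. It should still be corrected, because a named safety endpoint currently has two definitions.

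**What to change.** Before database lock, replace the quoted sentence in SAP 2.5.4 with:

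> If the AE start date or the vaccination date is missing or partially missing, time of onset is missing; a missing or partial stop date affects duration only.

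The sentence sits in the paragraph on unsolicited AEs, so the handling of solicited reactions is unaffected, and the rest of the subsection can stay. With this change an AE with a complete start date keeps its onset row whether or not it has ended, and onsets on D29-D35 stay out of the 28-day tables.

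The cost is one SAP sentence and a correction to any program already written to 2.5.4.

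As an optional side note, SAP 2.5.2.3 could say whether an SAE with a truly missing onset is counted in the 28-day SAE tables or only listed. That choice is the sponsor's, and the finding does not depend on it.

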#### ***Handling of immediate field for adverse events with missing***

For unsolicited non-serious systemic AEs, a missing response to the “Immediate” field is assumed to have occurred after the 30-minute surveillance period and will not be imputed.

For SAEs, missing or partially missing elapsed time from last vaccination recorded if within 24 hours will remain missing and not be imputed. Such SAEs will not be considered as immediate.

#### ***Handling of missing assessment of relationship of adverse events to investigational medicinal product***

Missing causality (relationship) for unsolicited non-serious AEs and SAEs will be considered at the time of analyses as related to vaccination, but no imputation should be done at the data level.

#### ***Handling of missing measurements of adverse events***

Partially missing temperatures will be handled as described in “Daily intensity” of [Section 2.5.2.1](#).

#### ***Handling of missing intensity adverse events***

For solicited reactions, missing intensities will be handled as described in “Daily intensity” of [Section 2.5.2.1](#). For unsolicited non-serious AEs, missing intensities will remain missing and will not be imputed.

#### ***Handling of potentially clinically significant abnormalities***

Not applicable.

#### ***Handling of immunogenicity data***

LLOQ and ULOQ management will be performed as described in [Section 2.5.3.1](#). No test or search for outliers will be performed. No replacement will be done for missing values.

### **2.5.5 Windows for time points**

Refer to [Table 1](#) for the allowance at each visit.

### **2.5.6 Unscheduled visits**

Unscheduled visit measurements of immunogenicity out of the allowance described in [Section 2.5.5](#) will not be analyzed.

## 2.5.7 Pooling of centers for statistical analyses

All data from each center will be pooled and analyzed as Enrolled subjects, Randomized subjects, PPAS, FAS and SafAS.

## 2.5.8 Statistical technical issues

### 2.5.8.1 Confidence interval for the individual group GMT and GMT ratio

The 2-sided 95% CI for the individual group GMT and GMTRs will be computed using the normal approximation as follows:

$$10^{(\bar{x} \pm t_{n-1, \alpha/2} \sqrt{v(\bar{x})})}$$

where  $10^{(\bar{x})}$  is the GMT,  $\bar{x} = \frac{1}{N} \sum \log_{10}(x)$ ,  $\log_{10}(x)$  is the log base 10 of the observed titer,  $N$  is the total observations in each vaccination group,  $\sqrt{v(\bar{x})}$  is the estimated standard deviation of  $\bar{x}$ ,  $\alpha = 0.05$ ,  $t_{n-1, \alpha/2}$  is the  $100(1 - \alpha/2)$  percentile of the central  $t$ -distribution with  $n-1$  degree of freedom.

### 2.5.8.2 Confidence interval for the GMT ratio between 2 groups

The calculations of the 95% CI for the GMT ratio between 2 groups are as following:

Logarithmic transformation of the individual titers will be calculated first. Assuming that individual  $\log_{10}(\text{titer})$  is normally distributed, the 95% CI for the difference in  $\log_{10}(\text{GMT})$  between group  $i$  and group  $j$  will be in the form:

$$\bar{X}_i - \bar{X}_j \pm t(1 - \alpha/2, n_i + n_j - 2) \cdot S \sqrt{1/n_i + 1/n_j}$$

where  $\bar{X}_i = \log_{10}(\text{GMT})$  is the mean of  $\log_{10}(\text{titer})$  of group  $i$ ,

$S^2 = [(n_i - 1)S_i^2 + (n_j - 1)S_j^2] / (n_i + n_j - 2)$  is the pooled sample variance,

$n_i$  and  $S_i^2$  are the sample size and sample variance of group  $i$ ,

$t(1 - \alpha/2, n_i + n_j - 2)$  is the  $100(1 - \alpha/2)$  percentile of the  $t$ -distribution with degrees of freedom (df) =  $n_i + n_j - 2$ .

### 2.5.8.3 Confidence interval for the single proportions

The 2-sided 95% CI for the single proportions will be constructed using the exact binomial method (Clopper-Pearson's method, quoted by Newcombe (2), i.e., using the inverse of the beta integral with SAS®):

$$\text{Lower bound: } 1 - \text{Beta}(1 - \alpha / 2, n - r + 1, r) \text{ and}$$

$$\text{Upper bound: } \text{Beta}(1 - \alpha / 2, r + 1, n - r),$$

where  $\alpha = 0.05$ , and  $r$  is the observed number of events/responders in  $n$  observations.

### 2.5.8.4 Confidence interval of the difference in proportions

The 2-sided 95% CI of the difference in proportions will be computed using the Wilson Score method without continuity correction, quoted by Newcombe (3) as follows:

Let  $\hat{\theta} = \pi_A - \pi_B$ , then if  $L = \hat{\theta} - \delta$  and  $U = \hat{\theta} + \varepsilon$  are respectively the lower and the upper limits of the CI, where:

$$\delta = Z_{0.025} \sqrt{\left\{ \frac{l_1(1-l_1)}{n_1} + \frac{u_2(1-u_2)}{n_2} \right\}}$$

$$\varepsilon = Z_{0.025} \sqrt{\left\{ \frac{l_2(1-l_2)}{n_2} + \frac{u_1(1-u_1)}{n_1} \right\}},$$

$l_1$  and  $u_1$  are calculated from the CI of the single proportion in group A given by:

$$\frac{\left( 2n_1 p_A + Z_{0.025}^2 \pm Z_{0.025} \sqrt{\left( Z_{0.025}^2 + 4n_1 p_A (1 - p_A) \right)} \right)}{2(n_1 + Z_{0.025}^2)},$$

$l_2$  and  $u_2$  are calculated from the CI of the single proportion in group B given by:

$$\frac{\left( 2n_2 p_B + Z_{0.025}^2 \pm Z_{0.025} \sqrt{\left( Z_{0.025}^2 + 4n_2 p_B (1 - p_B) \right)} \right)}{2(n_2 + Z_{0.025}^2)},$$

where  $Z_{0.025}$  is the upper 97.5th percentile of the standard normal distribution.

### **3 INTERIM ANALYSIS**

No interim analyses are planned. There will be 1 statistical analysis conducted after the end of the study (D28).

## 4 DATABASE LOCK

To keep the blinding of the vaccination (dose, route and site) information during the eCRF data review and immunogenicity assay, a 2-step database lock is planned as follows:

- Before 1st DBL:
  - SDV for blinded data, data review and deviation review need to be completed
  - Ongoing data lock for eCRF data (each CRF page)
- **1st DBL for eCRF data and Deviation**  
(except for Vaccination page and deviation related to vaccination, validity in immunogenicity and randomization anomalies by IRT system)
  - Actual vaccination information is still blinded at this time.
- After 1st DBL:
  - SDV for Unblinded Vaccination data (Consistency check between Unblinded source document and Blinded source document)  
If any data entry error is found, eCRF vaccination page (blinded data) will be updated. If it has impact on the deviation conclusion, DEVIAT file (blinded data) will be updated. (e.g., If the answer to “Administered as per Route provided by IRT?” at Vaccination page is changed to “No”, it impacts the DEVIAT file.)
  - Immunogenicity data release from GCI
- **2nd DBL for Immunogenicity data and eCRF Vaccination page** (also for DEVIAT if it is updated after 1st DBL)
- After 2nd DBL:
  - Key code release from Biostatistics & Programming
  - RANDO data release from IRT provider
  - “Unblinded TRTNO” data release from IRT provider  
“Unblinded TRTNO” includes detailed vaccination deviation/anomaly information. (e.g., the allocated route was IM, but the vaccine was actually administered by SC mistakenly.)

## **5 SOFTWARE DOCUMENTATION**

All summaries and statistical analyses will be generated using the SAS software, at least version 9.4 (SAS Institute, Cary, North Carolina, USA).

## **7 LIST OF APPENDICES**

Not applicable

